### **Study Design:**

A randomized, non-blinded trial with a crossover design will be used. Following informed consent and with appropriate subject assent, all subjects will have a screening visit. Following the screening visit, subjects with T1DM will undergo 3 studies: Part A (exenatide and long acting insulin), Part B (rapid and long acting insulin) and Part C (long acting insulin + rapid acting insulin + exenatide). **For Type 1 diabetes subjects who are on an insulin pump, for Part A they will be on their usual basal rate of rapid acting insulin and they would receive exenatide, for Part B they will be on their usual basal rate of rapid acting insulin and before they drink the boost milk shake, they will receive an insulin bolus according to their carbohydrate and sensitivity ratio's. For Part C they will be on their usual basal rate of rapid acting insulin and will also get exenatide and bolus of rapid acting insulin before they drink the boost milkshake.** The subjects will be admitted to the CRC on three separate occasions, at least 3-4 weeks apart. The three studies will be performed in a random order and the randomization will be done using a computerized system. The healthy controls will undergo a single study visit and will not receive any insulin or study drug. Except for the absence of diabetes, the healthy controls will be identical to the study subjects. Subjects with new onset diabetes will be compared to healthy controls. Inclusion Criteria: 1. Age between 12-18 years of age at the time of enrollment. 2. Diagnosed with antibody positive T1DM in the past 3 months. 3. Otherwise healthy except for their T1DM and treated hypothyroidism. 4. Females must have a negative pregnancy test. 5. Hemoglobin equal to or greater than 12 g/dl before each study. 6. Weight greater than 44 kg.

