Exclusion Criteria: 1. Any chronic disease: leukemia, inflammatory bowel disease, cystic fibrosis, juvenile rheumatoid arthritis etc, except for diabetes and hypothyroidism. 2. Any medications that may affect glucose metabolism. 3. Abnormal AST, ALT, amylase, lipase, creatinine (more than 3 times normal values). 4. Lack of a supportive family environment as detected by the clinicians and/or social workers. 5. History of substance abuse (evaluated by medical history and CRAFFT questionnaire which will be administered at the screening visit). 6. Positive pregnancy test in females. 7. Lactating and nursing mothers. The study will include 10 subjects with T1DM and 10 healthy controls. The study is designed to detect a 20% difference in mean area under the curve for glucose for a 270 min period (breakfast). From our previous protocols, we have found  $r > 0.8$  between repeated measures and that the standard deviation for our excursion measure AUC is approximately 30%. With these specifications, the necessary sample size is 8 subjects. With a 20% drop out rate, we would need 10 subjects with T1DM. We will also recruit 10 healthy controls for comparison. Study Procedure: Screening: After signing a consent form, a screening evaluation will be performed prior to study enrollment. The evaluation will consist of a detailed medical history and physical examination (including height, weight, vital signs and Tanner staging). Baseline laboratory tests will include: CBC, creatinine, AST, ALT, amylase, and lipase. In addition, healthy control subjects will have a diabetes antibody panel drawn. A urine pregnancy test will be performed in all female subjects. The approximate volume of blood drawn is expected to be 3 ml's for subjects with T1DM and 11 ml's for controls. Study: The subject must be NPO (except for water) for 8 hours prior to the study. The subject will be admitted at 0700. Vital signs, stat hemoglobin (if there is no documented hemoglobin in the past 28 days), and pregnancy tests (in females) will be checked. Hemoglobin must be  $>12$  g/dl and female subjects must have a negative urine pregnancy test. An intravenous line will be placed in the forearm. At around 0800 baseline blood samples will be drawn for: glucose, insulin, C-peptide, amylin, GLP-1, and glucagon. In Study A and C, blood for exenatide will also be drawn. If blood glucose values are below 70 mg/dl, IV glucose of 5-15 grams will be administered to achieve euglycemia (90-130 mg/dl). At around 0830 (0 min), the subjects with T1DM will get his/her home dose of long acting insulin (if it has not been administered the night before). **Insulin Pump users will be on their usual basal rate of rapid acting insulin.** For study part A, **Exenatide will be also be given as a subcutaneous injection of 1.25 mcg.** For study part B, **bolus of rapid acting insulin will also be given based on subjects prescribed regimen.** For study

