
part C, the subject will receive Exenatide 1.25 micrograms and rapid acting insulin (with a 30-50% reduction from the usual dose). No medication will be given to subjects in the control arm. Following this, the subject will be offered a standard liquid meal of Boost High Protein Drink, 12 Oz. (360 calories, 50 g of carbohydrates and 12 g of fat) and asked to consume it within a 10-15 minute period. This will be enriched with 1 gram of [1- 13C] glucose. Blood glucose concentrations will be measured at the bedside using an Analox glucose analyzer at -30, -10, 0, 10, 20, 30, 40, 50, 60, 70, 80, 90, 100, 110, 120, 130, 140, 150, 160, 170, 180, 200, 220, 240, 270, 300 min. Blood samples will be collected for hormonal analysis of Insulin, C-peptide, Amylin at -30, -10, 0, 10, 20, 30, 40, 60, 80, 120, 180, 240, 300 min. Samples for GLP- 1 will be collected at -30, 0, 10, 20, 40, 60, 80, 120, 180, 240, 300 min and Glucagon at -30, -10, 0, 10, 20, 30, 40, 60, 80, 100, 120, 140, 180, 240, 300 min. Blood samples for pK exenatide will only be collected in Study A and C at -30, 0, 10, 20, 40, 60, 120, 180, 240, 300 min. A total blood volume of 148.7 ml's will be drawn in study A and study C, and 128.7 ml's in study B and the control study. Expired 13CO2 will be determined in breath samples at 0, 20, 40, 60, 120, 180, 240, 300 min. During the study, if blood glucose values in a subject are less than 55 mg/dl, IV glucose of 5-15 grams will be administered to achieve euglycemia (90-130 mg/dl). 1-2 doses of IV glucose should correct hypoglycemia. If more than 3 doses are required to achieve euglycemia, the study will be terminated, the subject will be offered a meal tray and blood sugar rechecked to ensure euglycemia. If blood sugar at any time is more than 350 with moderate ketones, the study will be terminated. At the end of the study at 300 min, lunch will be provided (consistent carbohydrate meal) and insulin will be given as per the subject's prescribed regimen. The subject will be discharged home with a designated driver due to the risk of hypoglycemia. A subject will be withdrawn from participating in the study if he/she meets any of the following conditions: 1) develops a chronic disease 2) develops anemia 3) becomes pregnant 4) develops a weight loss of greater than 10 pounds for unspecified reasons 5) loss of contact- if we are unable to reach a study subject (within 2 months of screening or completion of the first study) by phone or mail to schedule the next appointment. All study subjects (that are withdrawn from the study) will receive a phone call and a letter notifying them that they have been withdrawn. Blood samples will be kept for 20 years because some of the assays have not been developed for some of the hormone analyses. Since it is difficult to perform clinical studies in pediatrics, we feel it is

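### Low priority: when T1DM visits are 21 to 28 days apart, the 28-day hemoglobin waiver can clear study 2 or 3 on a value taken before the previous study's blood draw

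*Protocol*

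**What the plan says.** All of the relevant text is in the Protocol, under Study Design.

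- **Floor.** Inclusion criterion 5 reads "Hemoglobin equal to or greater than 12 g/dl before each study". The admission checks repeat the limit as strictly above 12 g/dl; the difference does not matter here.
- **Which value counts.** At admission the check is a "stat hemoglobin (if there is no documented hemoglobin in the past 28 days"). The test comes before the IV line and the baseline samples. The only other scheduled source of a hemoglobin is the screening CBC: "Baseline laboratory tests will include: CBC, creatinine, AST, ALT, amylase, and lipase".
- **Visit spacing.** T1DM subjects are "admitted to the CRC on three separate occasions, at least 3-4 weeks apart". No maximum gap is given. Healthy controls have a single visit.
- **Blood taken.** "A total blood volume of 148.7 ml's will be drawn in study A and study C, and 128.7 ml's in study B"; the control study takes the same volume as study B.
- **Who.** Ages 12 to 18, "Weight greater than 44 kg". Numbers: "The study will include 10 subjects with T1DM and 10 healthy controls".
- **Withdrawal.** The conditions include "develops a chronic disease 2) develops anemia 3) becomes pregnant". Anemia is not given a threshold there.

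No hemoglobin is scheduled at the end of a study or between visits, and nothing requires a documented value to postdate the previous study's sampling.

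**The concern.** The floor is repeated for each study, and a subject who becomes anemic is withdrawn, so the protocol treats a change in hemoglobin between visits as important. The most foreseeable cause of such a change is the trial's own sampling. The look-back window (28 days) is at least as long as the shortest permitted gap between visits (21 days, or 28 on a stricter reading). The waiver can therefore remove the check at the visit where it would pick up the effect of the previous draw.

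At stake is a minor matter of participant safety. An adolescent slightly below the protocol's own floor could start another draw of 128.7 or 148.7 ml, with no scheduled hemoglobin at that visit to support the anemia withdrawal rule.

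**Working it through.** **1. Calendar rule.** Count only the tests the protocol requires: the screening CBC, plus a stat hemoglobin at admission, before the draw, when the latest value is more than 28 days old. Let *s* be the age of the CBC at study 1, and *g1* and *g2* the gaps from study 1 to 2 and from study 2 to 3. Call a visit exposed if the value that clears it was taken before the previous study's draw. A short gap is 21-28 days; a long gap is 29 days or more.

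- *Study 2* is exposed if the latest value is at most 28 days old at that visit. This needs a short *g1* and one of two conditions: *s* > 28, so that a stat test was done at study 1 and is now *g1* ≤ 28 days old; or *s* + *g1* ≤ 28, so that the CBC itself still counts.
- *Study 3* is exposed if *g2* is short and a stat test was done at study 2. If study 2 was itself waived, the latest value is at least 21 + 21 = 42 days old at study 3, so a new test is forced. Both visits can therefore never be exposed in one subject.

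To check this, all calendars with *s* = 0-90 (91 values), short gaps of 21-28 (8 values) and long gaps of 29-61 (33 values) were enumerated. The counts check the rule; they are not probabilities. The upper limits for *s* and the long gap are arbitrary, and the logic does not depend on them.

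| Gap 1 / gap 2 | Calendars | Study 2 exposed | Study 3 exposed | Neither |
|---|---|---|---|---|
| short / short | 91×8×8 = 5824 | 4256 | 1568 | 0 |
| long / short | 91×33×8 = 24024 | 0 | 24024 | 0 |
| short / long | 91×8×33 = 24024 | 17556 | 0 | 6468 |
| long / long | 91×33×33 = 99099 | 0 | 0 | 99099 |

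By hand for short/short: *s* > 28 gives 62×8×8 = 3968. *s* + *g1* ≤ 28 gives (8+7+…+1)×8 = 36×8 = 288. The sum is 4256, and the remaining 5824 − 4256 = 1568 are exposed at study 3. For short/long: 62×8×33 + 36×33 = 16368 + 1188 = 17556.

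If the spacing rule means a 4-week minimum, only a gap of exactly 28 days is exposed. With both gaps at exactly 28 days, one study is exposed at all 91 CBC ages (study 2 in 63, study 3 in 28). Every exposed visit has exactly one unchecked draw behind it.

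**2. Size of the drop.** The draw volumes and the 44 kg limit come from the protocol. Two assumptions do not: blood volume of 65-75 ml/kg, and no red-cell regeneration over 3 to 4 weeks, which makes the result an upper bound. The 60 and 70 kg weights are illustrative.

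Fraction lost *f* = draw / (weight × ml/kg). Fall from 12.0 = 12 × *f*. Start value that ends exactly at 12.0 = 12 / (1 − *f*).

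| Weight | *f*, smallest to largest | Fall (g/dl) | Start value ending at 12.0 |
|---|---|---|---|
| 44 kg | 128.7/3300 = 3.90% to 148.7/2860 = 5.20% | 0.47-0.62 | 12.49-12.66 |
| 60 kg | 128.7/4500 = 2.86% to 148.7/3900 = 3.81% | 0.34-0.46 | 12.35-12.48 |
| 70 kg | 128.7/5250 = 2.45% to 148.7/4550 = 3.27% | 0.29-0.39 | 12.30-12.41 |

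From 12.0 g/dl at 44 kg the end value is 11.53 to 11.38. If half the loss were made good by the next visit (also an assumption), the fall at 44 kg would be 0.23-0.31 g/dl and the limiting start value 12.24-12.32. With full recovery there is no exposure.

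**The case against.** A look-back window is an ordinary way to apply an eligibility floor, and the two hemoglobin statements do not contradict each other: one sets the limit and the other says which value meets it. Exposure turns on an ambiguous spacing phrase and shrinks to a single day on the 4-week reading. Since no maximum gap is set, the actual schedule may contain no exposed visit. The drop is computed without recovery, although some is to be expected in 3 to 4 weeks. Even the worst case, 11.4-11.5 g/dl, is about where a subject who starts one study at the floor would end it, and the protocol accepts that. Vital signs are checked at each admission, and anemia noticed clinically would still lead to withdrawal.

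Most of this stands, and it is why the point ranks low. It does not remove the gap. The protocol asks for the floor to be met before each study, and the window it chose can be satisfied by a value that the study's own sampling has made out of date. The 4-week reading still leaves a gap of exactly 28 days exposed, and four weeks to the day is a natural booking.

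**Conclusion.** The concern holds, as a low-priority participant-safety point. With a visit gap of 21 to 28 days, the waiver can clear study 2 or study 3 on a hemoglobin that predates the previous draw:

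- both gaps short: exactly one of the two studies is exposed;
- only the second gap short: study 3 always is;
- only the first gap short: study 2 is exposed for some screening dates and not for others;
- both gaps over 28 days: no exposure.

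This assumes no hemoglobin is obtained outside the protocol between visits. Controls are not exposed. At the weight limit, only T1DM subjects starting between 12.0 and about 12.5-12.7 g/dl could drop below the floor unseen, and fewer if red cells recover. With 10 such subjects, possibly nobody is affected. The sample size, the endpoint and the glucose AUC comparison are unaffected.

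**What to change.** In the admission checks under Study Procedure, add one clause: for studies 2 and 3, a documented hemoglobin from the past 28 days counts only if it was drawn after the previous study's blood sampling; otherwise a stat hemoglobin is done at admission. Leave the 28-day look-back as it is for study 1 and for controls.

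A value drawn on the same day, just after the previous sampling, would technically qualify, but no scheduled test produces one. Requiring a stat test at every study 2 and study 3 admission would close that too and is simpler to state.

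The clause adds one stat test for a T1DM subject when both gaps, or only the second, are 21 to 28 days; zero or one when only the first is; and none when both exceed 28 days. That is at most 10 × 1 = 10 extra tests in the trial, using a test already in the procedure, plus an occasional postponed visit.

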
cell mass in the pancreas. Our hypothesis is that exenatide can reduce postprandial glycemic excursions by twenty percent compared to insulin mono-therapy in children and adolescents with new onset type 1 diabetes. In addition, we would like to study the safety of this low dose of Exenatide (1.25 micrograms) in new onset type 1 diabetes. The specific aims of this study are to determine the following: 1. The role of exenatide as compared to insulin mono-therapy in reducing postprandial hyperglycemia. 2. The role of exenatide on postprandial glucagon and gastric emptying. 3. The effect of long acting insulin/ **rapid acting insulin on a basal rate in an insulin pump** on postprandial glucose excursions, glucagon concentrations and gastric emptying. 4. Postprandial glucose excursions, glucagon concentrations and gastric emptying in normal healthy controls.

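### No two treatment parts differ in exenatide alone, so neither an Aim 2 result nor a null Part C versus Part B difference can be attributed to exenatide by itself

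*Protocol*

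**What the plan says.** The hypothesis in the protocol's Background is that "exenatide can reduce postprandial glycemic excursions by twenty percent compared to insulin mono-therapy". Aim 1 is "The role of exenatide as compared to insulin mono-therapy in reducing postprandial hyperglycemia". Aim 2 is "The role of exenatide on postprandial glucagon and gastric emptying" and names no comparator.

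Study Design defines the parts for subjects with T1DM as "Part A (exenatide and long acting insulin), Part B (rapid and long acting insulin") and "Part C (long acting insulin + rapid acting insulin + exenatide"). It then repeats the definitions for pump users. In Part B "they will receive an insulin bolus according to their carbohydrate and sensitivity ratio's". In Part C they have their basal rate, exenatide and a bolus. Neither description of Part C mentions a smaller bolus.

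Study Procedure gives Part B the bolus of the subject's own regimen. For Part C it says "part C, the subject will receive Exenatide 1.25 micrograms and rapid acting insulin (with a 30-50% reduction from the usual dose"). It does not say how, when or by whom a value between 30% and 50% is settled. Study Design calls the trial non-blinded. Healthy controls attend once and receive neither insulin nor exenatide.

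**The concern.** Someone reading only Study Design would take Part C to be Part B plus exenatide, so that C-B would show what exenatide adds at an unchanged insulin dose. Under Study Procedure it does not, because the bolus is cut at the same visit.

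Two conclusions are at stake. For Aim 2, a difference between parts in glucagon or gastric emptying could come from exenatide, from the change in bolus, or from both. For glucose, exenatide and the cut would be expected to pull in opposite directions, so a small or null C-B could hide a real exenatide effect. Because the cut is a range, C-B may also average over different reductions in different subjects.

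**Working it through.** **The plan's own figure.** The only figure the protocol computes is the sample size, for a 20% difference in glucose AUC with SD 30% and r = 0.8 (the protocol says above 0.8). The protocol states neither alpha nor power; I assume two-sided 5% and 80%.

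- SD of the paired difference = 30 × √(2 × (1 − 0.8)) = 18.97%.
- n = ((1.960 + 0.842) × 18.97 / 20)² = 7.06, rounded up to 8, by the normal approximation.
- With 20% dropout, 8 / 0.8 = 10.

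The stated 8 and 10 reproduce, and the present point does not rest on them.

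**Layout under Study Procedure.**

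| Part | Exenatide | Bolus, % of usual |
|---|---|---|
| A | yes | 0 |
| B | no | 100 |
| C | yes | 50-70 |

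| Contrast | Change in exenatide | Change in bolus |
|---|---|---|
| A-B | added | 100% removed |
| C-B | added | 30-50% removed |
| C-A | none | 50-70% added |

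None of the three pairs differs in exenatide alone. The healthy controls cannot supply the missing contrast, because they do not have diabetes.

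**Spread within the range.** Two subjects can receive 70% and 50% of their usual bolus: 0.70 / 0.50 = 1.4-fold. If the bolus covers only the 50 g of carbohydrate in the meal (assumption: no correction component), the cut withholds the insulin for 0.30 × 50 = 15 g to 0.50 × 50 = 25 g.

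**What separating the two would need.** Let m be the mean outcome with basal insulin only, E the exenatide effect, b the effect of the full bolus and f the fraction cut. Assume additive effects and a linear bolus response.

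- A = m + E; B = m + b; C = m + E + (1 − f)b.
- A-B = E − b; C-A = (1 − f)b; C-B = E − f·b.
- Hence E = (C-B) + k(C-A), with k = f / (1 − f).
- k = 0.30/0.70 = 0.43 at a 30% cut, 0.40/0.60 = 0.67 at 40%, and 0.50/0.50 = 1.00 at 50%.
- The weight on C-A changes by 1.00 / 0.429 = 2.3-fold across the range.

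Three means are used to solve for three unknowns (m, E, b), so the part means leave nothing over to test additivity or linearity.

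**Reading a null C-B.** If C = B, then E = f·b, which is 0.3b to 0.5b. E is zero only if b is zero.

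**Reading a lower glucose AUC in C.** If the bolus does not raise AUC (b ≤ 0), then −f·b ≥ 0 and C-B ≥ E. A negative C-B therefore implies a negative E, and its size understates E. The documents give no sign for the bolus effect on glucagon or gastric emptying, so the same bound is not available for Aim 2.

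**The case against.** Several objections stand.

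- Study Design is an overview. It also leaves out the exenatide dose, which Study Procedure supplies. It omits the reduction without denying it. A reader might infer that the two sections contradict each other; the text supports only an omission to be reconciled.
- C-A holds exenatide fixed and varies only the bolus, so the trial carries its own check. If C-A is near zero for glucagon or gastric emptying, then under the formula above E is close to C-B whatever the cut, and the 2.3-fold change in weight hardly matters. The limit is that C-A spans 0 to 50-70% of the bolus, not the 50-70% to 100% step that separates C from B, and it rests on about 8-10 subjects.
- On glucose, the cut works against exenatide, so a lower AUC in C than in B still favours it in direction.
- The protocol nowhere says that a null C-B will be read as no effect, or names C-B as the Aim 2 contrast. A statistical analysis plan may define contrasts. It cannot supply a part that was not run, however, so the attribution limit on Aim 2 remains.

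Two stronger readings are tempting. One is that the hypothesis cannot be tested. It can, because the hypothesis and Aim 1 compare exenatide with insulin mono-therapy, and A-B and C-B are both comparisons of that kind between regimens. The other is that Aim 3, which studies insulin "on postprandial glucose excursions, glucagon concentrations and gastric emptying", shows that the bolus shifts the Aim 2 outcomes. Aim 3 concerns long acting insulin or the pump basal rate, which stay at their usual level in all three parts, so it says nothing about the meal bolus.

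**Conclusion.** The point holds in a limited form. By layout alone, and without any assumption, no pair of parts isolates exenatide. Aim 2 as worded therefore asks for something this design yields only with an assumed bolus dose-response. A null or small C-B on glucose is likewise not evidence of no exenatide effect.

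How far the cut shifts glucose, glucagon or gastric emptying is not in the documents, so no bias or power figure is given. The 1.4-fold dose spread follows directly from the stated range. The 15-25 g figure assumes a meal-only bolus, and the weights of 0.43 to 1.00 assume additivity and linearity; these figures illustrate the problem and do not estimate bias. The statement that a lower AUC in C favours exenatide assumes only that less bolus does not itself lower glucose.

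The missing rule within 30-50%, taken alone, would be a matter of detail. What gives the point weight is the conclusion that Aim 2 can support. Severity is minor to moderate.

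**What to change.** 1. Reconcile Study Design with Study Procedure so that the Part C bolus, and how its value is arrived at, is described once for pump and injection users. The dose and the rule are the sponsor's clinical decision.
2. Restate Aim 2 and its conclusions as regimen effects: A-B is exenatide in place of the bolus, and C-B is exenatide plus a reduced bolus against the usual bolus. State that a null C-B does not show absence of an exenatide effect.
3. Report C-A beside C-B for glucose, glucagon and gastric emptying as a within-trial check on whether the bolus moves these outcomes. Note the part of the bolus range it covers and the small number of subjects, and say that any estimate of exenatide at a fixed insulin dose rests on an assumed dose-response.

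This needs no extra subjects, visits or blood. The cost is a protocol clarification and a narrower claim for Aim 2.
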